### 4.1. *Justification for the Use of the Investigational Device in Human Subjects*

#### 4.1.1. Treatments for Aortic Stenosis

The incidence of aortic stenosis (AS) is increasing due to the aging of the world-wide population and the lack of drug therapies to prevent, halt, or effectively slow the stenotic process. Nearly 5% of individuals >75 years of age have some degree of AS. Once symptoms manifest, the prognosis is poor, especially when associated with congestive heart failure. Successful treatment of aortic valve obstruction can result in the improvement of symptoms, hemodynamic parameters, systolic function, and cardiac hypertrophy along with increased survival.

Surgical aortic valve replacement (SAVR) remains the gold standard treatment for the management of subjects with severe AS. However, the operative risk is increased in elderly subjects, in subjects with concomitant coronary artery disease or severely reduced left ventricular (LV) function, and in subjects with associated comorbidities such as cerebral and peripheral vascular disease, renal failure, and respiratory dysfunction. Percutaneous transluminal aortic valvuloplasty, which was introduced as an alternative to SAVR in elderly and/or high-risk subjects, can provide symptomatic relief and/or temporary improvement but does not provide definitive treatment in subjects with severe calcified AS. It is also associated with relatively high mortality and complication rates.

Transcatheter aortic valve replacement has recently emerged as an alternative to the surgical approach in the treatment of severe AS in subjects who are not suitable candidates for open-heart surgery. This technology is generally restricted to subjects considered at prohibitive or high surgical risk. Evidence of the safety of the procedure using either a balloon expandable or a self-expanding bioprosthetic heart valve has rapidly accumulated through observational studies, device-specific registries, national registries, and randomized controlled

trials. Through 2-year follow-up in the PARTNER US IDE trial there have been significant reductions in mortality and repeat hospitalization rates compared to standard medical therapy in subjects unsuitable for SAVR^29, and similar mortality rates compared to surgical valve replacement in high-surgical-risk subjects. An expert consensus document on TAVR was recently published.

Table 4.1-1 summarizes the peri-operative event rates through 30 days post-procedure from several TAVR studies that enrolled similar subjects as those planned for this study, as well as the results from the inoperable (Cohort B) and high risk (Cohort A) subjects with severe aortic stenosis enrolled in PARTNER. A more detailed summary of the available literature is presented in the Investigator Brochure.

**Table 4.1-1: Events from Peri-Operative to 30 Days (Transfemoral Approach)**

Study	Device/N	Death	MI	Major Stroke	Bleeding	Acute Kidney Injury	Vascular Complications
Webb, et al. 2006 	EW/18	11%	0%	0%	N/A	N/A	N/A
Webb, et al. 2007 	EW/50	12%	2%	4%	N/A	N/A	N/A
Webb, et al. 2009 	EW/113 a	8%	N/A	5.3%	11.6%	4.4%	8%
Osten, et al. 2010 	EW/16	6%	0%	6%	13%	0%	13%
Rodés-Cabau, et al. 2010 	EW/168 a	9.5%	0.6%	3.0%	N/A	N/A	N/A
Thomas, et al. 2010 	EW/463 a	6.3%	N/A	2.4%	9.9%	1.3%	22.9%
Leon, et al. 2010 	EW/267 b	5%	0%	5%	16.8%	1.1%	16.2% c 30.7%
Smith, et al. 2011 	EW/244 a,d	3.4%	0%	3.8%	9.3%	2.9%	14% c 22.7%
Lefèvre, et al. 2011 	EW/55	8.2%	3.3%	3.3%	23.5%	0%	28.4%
Grube, et al. 2006 	CV/25	20%	0%	4%	N/A	N/A	N/A
Grube, et al. 2007 	CV/86	12%	1%	10%	N/A	N/A	N/A
Piazza, et al. 2008 	CV/646	8%	0.6%	1.9% e	N/A	N/A	1.2%
Baan, et al. 2010 	CV/30	20%	0%	0%	N/A	N/A	N/A
Munoz-Garcia, et al. 2012 	CV/133 f	4.5%	0.8%	1.5%	N/A	N/A	2.2% c
Bullesfeld, et al. 2011 	CV/72 b,d,g	18.1%	5.6%	8.3% e	N/A	N/A	N/A
Buchanan, et al.	CV,	4.7%	1.3%	1.0%	33.1%	10.2% h	15.7% c

**Table 4.1-1: Events from Peri-Operative to 30 Days (Transfemoral Approach)**

Study	Device/N	Death	MI	Major Stroke	Bleeding	Acute Kidney Injury	Vascular Complications
2011 	EW/305						
Moat, et al. 2011 	CV, EW/599	5.5%	1.0%	4.0% i	N/A	N/A	6.2%
Stohr, et al. 2011 	CV/73 a EW/82 j	12% k	N/A	1.0%	N/A	4.0%	N/A
Zahn, et al. 2011 	CV, EW/697 l	12.4%	0.3%	2.8% e	N/A	N/A	17.1% m
Bosmans, et al. 2011 	CV/133 a EW/99 a	8% (CV); 6% (EW)	N/A	5% e,n	N/A	6% n,o	N/A
Tamburino, et al. 2012 	CV, EW/218 p	6.9%	0.0%	2.3%	5.5%	N/A	N/A
Gilard, et al. 2012 	CV, EW/2361 a	8.5%	0.8%	2.2%	1.2% q	N/A	5.5% c

a: Transfemoral approach population only

b: Inoperable subjects

c: Major

d: High risk subjects

e: All stroke

f: Femoral access in 90.9% of cases

g: Femoral access in 98% of cases

h: Stage 3

i: In hospital

j: Apical access only

k: Includes apical and transfemoral

l: 92.4% transfemoral and 3.2% subclavian; 84% of all procedures were CV

m: Groin problem with need of transfusion

n: All subjects

o: Dialysis

p: Femoral access in 97.2% of cases

q: Life-threatening bleeding

Abbreviations: CV=CoreValve; EW=Edwards; MI=myocardial infarction; N/A=not available

#### 4.1.2. REPRIZE I Study

The aforementioned results notwithstanding, TAVR with early generation devices has been associated with increased stroke risk versus surgical valve replacement. Cerebrovascular accidents and vascular complications associated with TAVR have been significant predictors of mortality. The paravalvular regurgitation more commonly seen with TAVR compared to surgery has also been accompanied by higher early and late mortality. While careful subject selection may serve to mitigate these risks, device design improvements such as seen with the Lotus Valve System (Section 5.1) may enable more precise placement,

minimize or eliminate paravalvular regurgitation, and obviate the need for valve-in-valve repeat intervention.

The prospective, single arm, multicenter REPRISE I (REpositionable Percutaneous Replacement of Stenotic Aortic Valve through Implantation of Lotus™ Valve SystEm) feasibility study (N=11) assessed the acute safety and performance of the Lotus Valve System in symptomatic subjects with calcified stenotic aortic valves who were considered high risk for surgical valve replacement. The primary endpoint was clinical procedural success, defined as successful implantation of a Lotus Valve (per the Valve Academic Research Consortium [VARC] definitions) without in-hospital major adverse cardiovascular and cerebrovascular events (MACCE, defined as all-cause mortality, periprocedural myocardial infarction  $\leq 72$  hours after the index procedure, major stroke, urgent/emergent conversion to surgery or repeat procedure for valve-related dysfunction) through discharge or 7 days post-procedure, whichever came first. Clinical follow-up will extend through 5 years.

The primary endpoint was achieved in 9/11 subjects. The device was successfully implanted in all 11 subjects but there was a device failure in 1 subject based on not meeting one of four VARC criteria for device success. The Echocardiography Core Lab concluded that the device failure (mean aortic valve gradient  $>20$  mmHg) resulted from a hyperdynamic state in the subject and noted that the prosthetic valve appeared to be functioning well. Ten (10) of 11 subjects had no in-hospital MACCE; there were no deaths and 1 major stroke. Paravalvular regurgitation at discharge TTE was mild in 2 subjects, trivial in 1 subject, and absent in the other 8 subjects; these outcomes compare favorably with published data.

To date, data are available through 6 months. There were no additional MACCE events beyond the primary endpoint. While all REPRISE I subjects were NYHA Class II (n=6) or Class III (n=5) at baseline, this distribution was significantly improved at 6 months (6 in Class I, 4 in Class II, 1 in Class III;  $P=0.004$ ). The mean aortic valve gradient was  $13.9 \pm 3.8$  mmHg for the cohort at 6 months, which was below the VARC criterion of 20 mmHg, and there was no moderate or severe paravalvular aortic regurgitation. The results of the REPRISE I feasibility study support the acute safety and performance of the Lotus Valve System.

#### **4.2. Justification for the Study Design**

As noted above, the Lotus Valve System potentially provides a number of performance and safety features beyond that of earlier TAVR devices. These include a pre-loaded delivery system, early leaflet function to maintain hemodynamic stability during valve deployment, an enhanced ability to place the valve correctly at the first attempt using the radiopaque marker to aid in valve positioning, the capacity to reposition the device if the initial deployment is considered to be suboptimal, the ability to retrieve the device if during the procedure the decision is made not to implant, and the aforementioned outer seal designed to minimize paravalvular leakage. The anticipated risks and benefits associated both with the Lotus Valve System and with participation in this clinical investigation are summarized in the Investigator

Brochure and in Section 19 of this document. The conclusion of this risk-benefit analysis demonstrates that the known risks associated with the procedure and the specific use of the Lotus Valve System have been mitigated to acceptable limits and are comparable to that associated with existing transcatheter aortic valves. It was also concluded that the aforementioned design features may improve procedural safety. The available sponsor-provided training program and proctorship for physicians further mitigates the risk. The result is a procedure with residual subject risk comparable to that of currently available transcatheter aortic valves and significant potential benefit compared with other alternatives.

It is therefore determined that:

- All applicable risks have been addressed through appropriate testing and any residual risks are acceptable when weighed against the potential benefits to the subject.
- The potential benefits of the use of the device out-weigh the risks.

## 5. Device Description

### 5.1. Lotus Valve System

The Lotus Valve System (Figure 5.1-1) has two main parts: a bioprosthetic aortic valve implant and a catheter-based delivery system for introduction and delivery of the valve implant. The device is introduced percutaneously via the femoral artery using conventional catheterization techniques. Femoral access using the surgical cut-down approach can also be performed to gain access into the aortic vessel. More detailed product information is contained in the Investigator Brochure and Instructions for Use (IFU).

[figure not shown]

Figure 5.1-1: Lotus™ Valve System

[figure not shown]
### 5.1.1. Lotus Valve

The Lotus Valve (Figure 5.1-2) consists of 3 bovine pericardial leaflets. The commissures of the leaflets are attached to the valve frame through portions of the locking components.

The valve frame is made of a single nitinol wire strand woven into a braided structure. The wire ends of this frame are encapsulated by a tantalum crimp that is used as a radiopaque marker, and which is located in the center of the frame height. The braided structure is designed to foreshorten and expand radially when delivered, and is then locked in this position using a post and buckle locking mechanism.

The Adaptive™ Seal is made of a polyurethane/polycarbonate blend and is located on the outside bottom half of the frame. This seal provides a barrier between the native annulus and the frame to help reduce paravalvular leakage.

The valve is deployed in a beating heart and rapid pacing is not required during valve deployment. The valve begins to function early in the deployment process, providing stabilized hemodynamic functionality.

**Figure 5.1-2: Lotus Valve Implant**

The device is designed so that the radial strength of the frame produces a specified final “as-deployed” diameter (23 mm or 27 mm) when the valve is locked, regardless of the target annulus. The frame height of both valve sizes in the deployed state is approximately 19 mm.

### 5.1.2. Lotus Delivery System

The Lotus Delivery System is made of the catheter and the handle.

- The catheter is a sheath in which mandrels allowing the shortening, locking, unlocking, and elongation of the valve, as well as its releasing, connect from the handle to the valve.

The catheter has a hydrophilic coating to facilitate the insertion. The tip of the catheter seats on the shoulder of a nosecone to provide a smooth transition.

- The handle is shown in
- Figure 5.1-3.
  - The handle has 3 ports; 2 of the ports are for flushing purposes and one is the Guidewire Port.
  - The Control Knob at the proximal end of the handle is the primary control used to deploy the valve. It operates both the sheathing/unsheathing function as well as the locking/unlocking function.
    - The sheathing/unsheathing capability allows the implant to be pulled into or pushed out of the outer catheter.
    - The locking function shortens the valve implant into the locked configuration; the unlocking function elongates the valve.
  - The Release Collar is used when the operator is ready to release the valve. A sliding door covers the collar to avoid inadvertent premature release.

**Figure 5.1-3: Lotus Valve Delivery System – Handle**

## 5.2. *Intended Use*

The Lotus Valve System is intended to improve aortic valve function for symptomatic subjects with severe calcific aortic stenosis (aortic valve area [AVA] of  $<1.0 \text{ cm}^2$  or AVA index of  $<0.6 \text{ cm}^2/\text{m}^2$ ) who are at high risk for standard surgical valve replacement.

## 5.3. *Device Labeling*

The study Manual of Operations includes the IFU for the Lotus Valve System. Study devices are labeled on the top and one side (one label wraps around the top and side) of the outer carton and on the sterile pouch. Packaging will include peelable, self-adhesive labels for each unit shipped. The labeling will include the following information.

- Product Name
- Part/Reference number
- Lot number (matches the lot number on the handle)
- Valve size
- Expiration (use by) date (labeled as month/year, device not to be used after the last day of the indicated month)
- Temperature storage requirements

The following statement appears on the label.

**CAUTION: Exclusively for Clinical Investigations.**

Device labeling will be provided in local language(s) as per respective national regulations.

## 6. Objectives

The objective of the REPRISE II study is to evaluate the safety and performance of the Lotus™ Valve System for transcatheter aortic valve replacement (TAVR) in symptomatic subjects with severe calcific aortic stenosis who are considered high risk for surgical valve replacement.

## 7. Endpoints

### 7.1. *Primary Endpoints*

The primary device performance endpoint is the mean aortic valve pressure gradient at 30 days post implant as measured by echocardiography and assessed by an independent core laboratory. The primary analysis population will be the subject population implanted with the

Lotus Valve. Outcomes in this as-treated subject population in the main trial cohort (N=120) will be compared to a performance goal (PG; see Section 12.1.1.1).

The primary safety endpoint is all-cause mortality at 30 days after the implant procedure. The primary safety endpoint will be evaluated on an intention-to-treat (ITT) basis (all subjects enrolled, whether or not a study device is implanted). Outcomes in the combined main and extended trial cohort (N=250) will be compared to a PG (see Section 12.1.1.3).

### 7.2. *Secondary Endpoints*

Secondary endpoints are listed below and will be evaluated on an ITT basis. Definitions can be found in Table 26.2-1.

- Effective orifice area at 30 days as measured by echocardiography and assessed by an independent core laboratory
- Device performance endpoints peri- and post-procedure:
  - Successful vascular access, delivery and deployment of the Lotus Valve System and successful retrieval of the delivery system
  - Successful repositioning (partial or complete resheathing of the Lotus Valve in the catheter and redeployment in a more accurate position within the aortic valve annulus) of the Lotus Valve System if repositioning is attempted
  - Successful retrieval (complete resheathing of the Lotus Valve in the catheter and removal from the body) of the Lotus Valve System if retrieval is attempted
  - Grade of aortic valve regurgitation: paravalvular, central and combined
- Device Success post implant procedure based on the VARC definitions

**Note:** At least 1 echocardiogram must be obtained before discharge or 7 days (whichever comes first); if multiple echocardiographic studies are performed prior to discharge and within 7 days of the procedure, the latest study performed will be used for analysis.

### 7.3. *Additional Measurements*

Additional measurements based on the VARC endpoints and definitions (see references and Table 26.2-1 in the Appendix for definitions) will be collected peri- and post-procedure, at discharge or 7 days post-procedure (whichever comes first), 30 days, 3 months, 6 months, and 1, 2, 3, 4, and 5 years post index procedure, unless otherwise specified below. Data will be evaluated on an ITT basis.

- Safety endpoints adjudicated by an independent Clinical Events Committee (CEC):
  - Mortality: all-cause, cardiovascular, and non-cardiovascular
  - Stroke: disabling and non-disabling
  - Composite of all-cause mortality and disabling stroke
  - Myocardial infarction (MI): periprocedural  $\leq 72$  hours post index procedure) and spontaneous ( $>72$  hours post index procedure)

- Bleeding: life-threatening (or disabling) and major
- Acute kidney injury ( $\leq 7$  days post index procedure): based on AKIN System Stage 3 (including renal replacement therapy) or Stage 2
- Major vascular complication
- Repeat procedure for valve-related dysfunction (surgical or interventional therapy)
- Hospitalization for valve-related symptoms or worsening congestive heart failure (NYHA class III or IV)
- New permanent pacemaker implantation resulting from new or worsened conduction disturbances (including left bundle branch block [LBBB] and third degree atrioventricular block)
- New onset of atrial fibrillation and atrial flutter
- Coronary obstruction (periprocedural)
- Ventricular septal perforation (periprocedural)
- Mitral apparatus damage (periprocedural)
- Cardiac tamponade (periprocedural)
- Prosthetic aortic valve malapposition, including valve migration, valve embolization, ectopic valve deployment, or transcatheter aortic valve (TAV)-in-TAV deployment
- Prosthetic aortic valve thrombosis
- Prosthetic aortic valve endocarditis
- Prosthetic aortic valve performance as measured by transthoracic echocardiography (TTE) and assessed by an independent core laboratory, including effective orifice area, mean and peak aortic gradients, peak aortic velocity, and grade of aortic regurgitation
- Functional status as evaluated by the following:
  - 5-m gait speed test (at 1 year compared to baseline)
  - New York Heart Association (NYHA) classification
- Neurological status as determined by the following:
  - National Institutes of Health Stroke Scale (NIHSS) at discharge and 1 year
  - Modified Rankin Scale (mRS)
- Health status as evaluated by SF-12 and EQ-5D Quality of Life (QOL) questionnaires at baseline; 1 and 6 months; and 1, 3, and 5 years

**Note 1:** The VARC safety composite at 30 days will be reported. This includes all-cause mortality, all stroke, life-threatening bleeding, acute kidney injury Stage 2 or 3, coronary artery obstruction requiring intervention, major vascular complication, and repeat procedure for valve-related dysfunction.

**Note 2:** The VARC efficacy composite at 1 year will be reported. This includes all-cause mortality (after 30 days), all stroke, requiring hospitalization for valve-related symptoms or worsening congestive heart failure (NYHA class III or IV), and prosthetic heart valve

dysfunction (mean aortic valve gradient  $\geq 20$  mm Hg, effective orifice area  $\leq 0.9$ - $1.1$  cm^2 and/or Doppler velocity index [DVI]  $< 0.35$ , AND/OR moderate or severe prosthetic valve aortic regurgitation [per VARC definition]).

**Note 3:** Time-related valve safety composite will be reported. This includes structural valve deterioration (valve-related dysfunction requiring repeat procedure [TAVR or SAVR]), prosthetic valve endocarditis, prosthetic valve thrombosis, thromboembolic events (e.g., stroke), and VARC bleeding (unless clearly unrelated to valve therapy based on investigator assessment).

**Note 4:** In the main trial cohort (N=120), for subjects diagnosed with a neurological event (e.g., stroke, transient ischemic attack), a neurological physical exam, NIHSS assessment, and mRS must be performed after the event; mRS must also be administered at 90 days post-neurological event (see Table 11.1-1). Among the 130 subjects subsequently enrolled (extended trial cohort), for subjects diagnosed with a neurological event, NIHSS assessment and mRS must be performed after the event; mRS must also be administered at 90 days post-neurological event; the neurological physical exam is not required (see Table 11.1-2).

**Note 5:** The VARC clinical efficacy composite includes the need for hospitalization associated with valve-related symptoms or worsening congestive heart failure (CHF) as a basis for calculation of a “days alive outside the hospital” endpoint. This includes heart failure, angina, or syncope due to aortic valve disease requiring intervention or intensified medical management; clinical symptoms of CHF with objective signs including pulmonary edema, hypoperfusion, or documented volume overload AND administration of intravenous diuresis or inotropic therapy, performance of aortic valvuloplasty, institution of mechanical support (intra-aortic balloon pump or ventilation for pulmonary edema), or hemodialysis for volume overload; clear documentation of anginal symptoms AND no clinical evidence that angina was related to coronary artery disease or acute coronary syndrome; documented loss of consciousness not related to seizure or tachyarrhythmia.

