Unanticipated Serious Adverse Device Effect (USADE) Ref: ISO 14155:2011	Serious adverse device effect which by its nature, incidence, severity or outcome has not been identified in the current version of the risk analysis report 
Note: Anticipated serious adverse device effect (ASADE) is an effect which by its nature, incidence, severity or outcome has been identified in the risk analysis report.

Device Deficiency Ref: ISO 14155:2011 Ref: MEDDEV 2.7/3 12/2010	A device deficiency is any inadequacy of a medical device with respect to its identity, quality, durability, reliability, safety or performance. 
Note 1: Device deficiencies include malfunctions, use errors, and inadequate labeling.
 
Note 2: All device deficiencies that could have led to a SADE if a) suitable action had not been taken or b) if intervention had not been made or c) if circumstances had been less fortunate shall be reported as required by the local IRB/EC, national regulations, or the protocol.

a: Other definitions may apply per local reporting requirements.

Underlying diseases are not reported as AEs unless there is an increase in severity or frequency during the course of the investigation. Death should not be recorded as an AE, but should only be reflected as an outcome of a specific SAE (see Table 21.1-1 for AE definitions).

In-patient hospitalization is defined as the subject being admitted to the hospital, with the following exceptions.

- A hospitalization that is uncomplicated and elective/planned (i.e., planned prior to enrollment) does not have to be reported as an SAE.
- If complications or AEs occur during an elective/planned (i.e., planned prior to enrollment) hospitalization after enrollment, the complications and AEs must be reported as AEs or SAEs if they meet the protocol-specified definitions.

Any AE experienced by the study subject beginning from the time of Lotus Introducer sheath insertion, whether during or subsequent to the procedure, must be recorded in the eCRF.

Refer to Section 19 for the known risks associated with the study device(s).

Based on the VARC recommendations and definitions, the adverse events and/or safety endpoints requiring adjudication by the CEC include but are not limited to the following.

- Mortality: all-cause, cardiovascular, and non-cardiovascular
- Neurologic event: disabling or non-disabling stroke, and TIAs

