- Myocardial infarction (MI): periprocedural ( $\leq 72$  hours post index procedure) and spontaneous ( $> 72$  hours post index procedure)
- Bleeding events: life-threatening (or disabling), major and minor
- Acute kidney injury ( $\leq 7$  days post index procedure): based on AKIN System Stage 3 (including renal replacement therapy), Stage 2, and Stage 1
- Vascular complications: major and minor
- Repeat procedure for valve-related dysfunction (surgical or interventional therapy)
- Hospitalization for valve-related symptoms or worsening congestive heart failure (NYHA class III or IV)
- New permanent pacemaker implantation resulting from new or worsened conduction disturbances (including new left bundle branch block [LBBB] and third degree atrioventricular block)
- New onset of atrial fibrillation or atrial flutter
- Coronary obstruction (periprocedural)
- Ventricular septal perforation (periprocedural)
- Mitral apparatus damage (periprocedural)
- Cardiac tamponade (periprocedural)
- Prosthetic aortic valve malapposition, including valve migration, valve embolization, ectopic valve deployment, or transcatheter aortic valve (TAV)-in-TAV deployment
- Prosthetic aortic valve thrombosis
- Prosthetic aortic valve endocarditis

Details on the CEC events and procedures are outlined in the CEC charter. Tests and images required to adjudicate these events are specified in the event definitions (see Table 26.2-1).

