#### **22.1.1. Clinical Events Committee**

A CEC will be used in this study. A CEC is an independent group of individuals with pertinent expertise, including cardiovascular interventional therapy, cardiovascular surgery, and neurology, which reviews and adjudicates important endpoints and relevant adverse events reported by study investigators. The CEC will review a safety event dossier, which may include copies of subject source documents provided by study sites, and adjudicate study endpoint related clinical events. The responsibilities, qualifications, membership, and committee procedures of the CEC are outlined in the CEC charter.

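### The time-related valve safety composite drops bleeds on the investigator's judgement alone, with no documented independent review of the exclusion (minor)

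*Combined protocol and SAP*

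**What the plan says.** Section 7.3, Note 3 states "Time-related valve safety composite will be reported" and lists its components: structural valve deterioration, prosthetic valve endocarditis, valve thrombosis, thromboembolic events and, last, "VARC bleeding (unless clearly unrelated to valve therapy based on investigator assessment". The synopsis (Section 2) repeats the note. No other component carries an investigator filter.

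The same section has a separate list headed "Safety endpoints adjudicated by an independent Clinical Events Committee (CEC", in which bleeding appears as "Bleeding: life-threatening (or disabling) and major". Section 21.1 is wider. It says "the adverse events and/or safety endpoints requiring adjudication by the CEC include but are not limited to the following" and the list includes "Bleeding events: life-threatening (or disabling), major and minor". Section 22.1.1 describes the committee: "A CEC is an independent group of individuals with pertinent expertise". On procedure, Section 21.1 says only "Details on the CEC events and procedures are outlined in the CEC charter", and the charter is not part of the documents.

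Section 21.2 asks the investigator to classify each adverse event as related or unrelated to the study device, using Table 21.2-1. Section 12.1.2 plans no inference on the additional endpoints.

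**The concern.** The investigator implants the valve, follows the subject and, in a single-arm study, always knows the treatment. Note 3 lets that person decide that a bleed does not count in a safety composite. The decision works in one direction only: an exclusion can take an event out and can never add one. If some exclusions are wrong, the reported composite looks better than it should, and a reader of the study report has no means of seeing by how much.

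At stake is the credibility of one descriptive safety result in a study that follows implanted subjects for up to 5 years. No test or success criterion depends on it.

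**Working it through.** The plan states no expected rate, performance goal or sample size for this composite, so there is no figure to reproduce. The check is mainly a comparison of texts.

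**1. Who judges what.**

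| Question | Who decides | Source |
|---|---|---|
| Did a VARC bleed occur, and how severe was it? | CEC: life-threatening, major and minor | Section 21.1 (Section 7.3 names the first two only) |
| Is an adverse event related to the device? | Investigator | Section 21.2 |
| Is a bleed clearly unrelated to valve therapy, and so left out of the composite? | Investigator | Note 3, Sections 2 and 7.3 |
| Does anyone independent check the third decision? | Not stated | CEC procedures are left to the charter |

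Endocarditis, valve thrombosis, stroke and repeat procedure are all on the CEC list in Section 21.1, with no investigator opt-out in Note 3.

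**2. Is the criterion defined?** Note 3 refers to valve therapy and gives no definition. Table 21.2-1 is the only set of relatedness criteria, and it concerns the investigational product. Its unrelated class covers events attributed to another drug. Sections 11.6 and 11.8 require antiplatelet treatment around and after the implant. An investigator who borrowed Table 21.2-1 could therefore class a bleed on that treatment as unrelated, while a colleague who reads valve therapy more broadly could keep it. Both readings fit the text.

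**3. Direction.** Write b for the proportion of subjects with a VARC bleed, e for the share of those excluded, w for the share of exclusions that are wrong, and u for the share of wrongly excluded subjects with no other qualifying event. Then

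bias in the composite rate = −(b × e × w × u).

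Every factor lies between 0 and 1, so the bias is zero or negative. A negative value favours the device.

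**4. Size.** The documents give none of e, w or u, and give b only for other devices at 30 days (Table 4.1-1). The bound b × e sets w = u = 1, meaning that every exclusion is wrong and no subject has another component event. With N = 250 and e assumed at 10% to 50%:

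| b, from Table 4.1-1 | Subjects with a bleed (250 × b) | Subjects removed at e = 10% to 50% | Largest fall in the rate |
|---|---|---|---|
| 1.2% (life-threatening only, footnote q) | 3.0 | 0.3 to 1.5 | 0.12 to 0.60 points |
| 9.9% | 24.8 | 2.5 to 12.4 | 0.99 to 4.95 points |
| 33.1% | 82.8 | 8.3 to 41.4 | 3.31 to 16.55 points |

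For example, 0.099 × 0.10 = 0.0099, or 0.99 points. The spread, from about a tenth of a point to more than 16 points, shows that the documents do not fix the size. The rates also mix bleeding definitions and stop at 30 days, while the additional measurements run to 5 years. These are ceilings under stated assumptions and not estimates of bias.

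**The case against.** The strongest reply is that Note 3 is consistent with the rest of the plan. Section 21.2 already gives device relatedness to the investigator, the default in Note 3 is to count the bleed, and only clearly unrelated bleeds leave. Removing bleeds that truly have nothing to do with the valve is what such a composite is meant to do. All of this stands. It means that bias is a possibility and not a finding.

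A reader might infer that the investigator overrides a CEC ruling, since the CEC adjudicates bleeding. The documents do not support that. They show the CEC adjudicating bleeding events and do not say that it judges their relation to valve therapy. The list in Section 21.1 is open-ended, and the charter may or may not cover it. What remains is narrower: no independent review of the exclusion is documented. The task would fit the committee, which already separates cardiovascular from non-cardiovascular death and adjudicates hospitalization for valve-related symptoms.

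A reader might also infer that the composite is offered as a CEC-adjudicated endpoint. It is not. It stands in a separate note after the CEC list, and the note names the investigator as assessor.

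Finally, serious bleeds stay visible elsewhere. Life-threatening and major bleeding is reported on its own, and the 30-day VARC safety composite (Note 1) counts life-threatening bleeding without a relatedness filter. This limits the harm but does not remove the gap: components overlap within subjects, so separate bleeding rates do not let a reader rebuild the composite with every bleed counted.

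**Conclusion.** The point holds in a limited form and is minor. The treating investigator, who knows the treatment, alone decides which VARC bleeds leave the composite. The criterion is undefined, and no independent review of the decision is documented, although an independent committee already adjudicates the bleeds themselves. Any error would favour the device.

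It would be wrong to say that the composite is biased. That needs wrong exclusions, and the documents give no sign of how often they would occur. The size cannot be derived. The composite carries no hypothesis, performance goal or alpha, and neither the 30-day gradient nor the 30-day mortality conclusion depends on it. The conclusion rests on the protocol text alone; a CEC charter that already assigns this decision to the committee would largely answer it, leaving Note 3 to be brought into line.

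**What to change.** 1. In Note 3, in both Section 2 and Section 7.3, replace the investigator's assessment with CEC adjudication, so that a bleed is left out only when the CEC finds it clearly unrelated to valve therapy.
2. Define that criterion in the CEC charter, and say how bleeds on protocol-required antiplatelet treatment are to be classed. Table 21.2-1 cannot serve as it stands, because it covers only the investigational product.
3. Report the composite a second time with all CEC-adjudicated VARC bleeds included, as a sensitivity result. The difference between the two shows how much the exclusion matters.

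The cost is a wording change, a charter entry and a field on the adjudication form. The CEC would also have to re-review, for relatedness, bleeds it has already adjudicated; the change table for version AF cites observations from the ongoing study, so some may exist. The sensitivity result uses data already being collected.
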